1.3.4.2 Summary of CX-2009 Clinical Efficacy

As of 30 November 2019, 2 out of 92 (2.2%) response-evaluable subjects had a confirmed partial response (PR), 6 out of 92 (6.5%) had unconfirmed PRs, and 21 out of 92 (22.8%) achieved stable disease ([SD]; at least 1 on-study scan with SD).

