7.1 Interim Analyses

No formal interim analysis is planned.

Administrative interim analyses on safety and efficacy or on PK, immunogenicity, and selected biomarkers may be performed several times prior to completion of the study in order to facilitate program decisions and to support study presentations or publications.

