10.1 General Statistical Methodology

Data will be analyzed using SAS (Version 9.4 or higher). All consented subjects are identified by an 8-digit Subject Number where the first four digits represent site and the last four digits are the sequential enrollment within a site (e.g. 1234-0001).

Descriptive statistics will be tabulated as follows:

- Categorical data will be summarized in contingency tables presenting frequencies and percentages.
- Continuous data will be summarized using number of non-missing values (n), mean, median, standard deviation, and median and range values. Where relevant, Q1 and Q3 may be presented.

The tables will be created by dose level and by cancer type, unless otherwise specified. For tables by dose level, all available data from Parts A, A2, and B will be pooled with ≤ 2 mg/kg presented as a single dose group and 4, 5, 6, 7, 8, 9, 10 mg/kg presented as separate dose groups; Part C1 dosing 4 mg/kg Q2W and 6

mg/kg Q2W will also be presented as separate dose groups. Data from planned, protocol-specified visits and unplanned visits will be included in listings, unless otherwise noted. Baseline tables will contain a total column when appropriate.

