13.1.2 Secondary Efficacy Endpoints

Secondary efficacy endpoints are:

- DOR,
- TTR,
- PFS, and
- OS.

Time-to-Event Endpoints

DOR

DOR is defined as the time from the date of the first documentation of objective tumor response (i.e., ORR = CR or PR) that is subsequently confirmed to the date of the first documentation of objective disease progression or death due to any cause, whichever occurred first. DOR is only calculated for subjects in the REP who have a confirmed objective tumor response. Subjects who neither progress nor die will be censored on the date of their last tumor assessment.

Table 2 Date of Censoring – DOR

| Description of Situation | Date of Progression or Censoring | Outcome |
|---|---|----------------|
| No disease progression nor death on-study | Date of last tumor assessment | Censored |

TTR

TTR is defined as the time from the date of the first dose of study drug to first documentation of confirmed objective tumor response. TTR is only calculated for subjects in the REP.

PFS

PFS is defined as the time from the date of the first dose of study drug to the date of first documentation of objective tumor progression (i.e., PD) or death due to any cause, whichever occurs first. Subjects who die without a reported progression will be considered to have progressed on the date of their death. Subjects who did not progress or die will be censored on the date of their last tumor assessment. Subjects who did not have any on-study tumor assessments and did not die will be censored on their date of first dose of study treatment. Subjects who started anti-cancer therapy without a prior reported progression will be censored on the date of their last tumor assessment prior to the initiation of subsequent anti-cancer therapy. PFS is calculated for using the SP.

Table 3. Date of Progression or Censoring -- PFS

| Description of Situation | Date of Progression or Censoring | Outcome |
|---------------------------------|---|----------------|
| No baseline disease assessments | Date of first dose of study drug | Censored |

| | | |
|---|---|------------|
| Death before first disease assessment | Date of death | Progressed |
| No disease progression nor death on-study | Date of last tumor assessment with a response assessment other than not evaluable | Censored |
| Death without a reported progression | Date of death | Progressed |
| No on-study tumor assessments and did not die | Date of first dose of study drug | Censored |

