Estimates of time-to-event endpoints (DOR, TTR, PFS, and OS) will be obtained using the Kaplan-Meier method. Kaplan-Meier curves will be provided for these endpoints. A swim lane plot will be provided for DOR. DOR and TTR will also be summarized using descriptive statistics for confirmed objective responders.

The median, and 95% CIs around the DOR, TTR, PFS, and OS will also be calculated using the Kaplan-Meier method. The range of TTR, PFS and OS will be provided as well. Frequencies and percentages will be summarized for event rates and censored observations of the time-to-event endpoints. Six- and twelve-month and 2-year survival rates will be included as well. The number and percentage of disease progressions and deaths will be included (replacing the event rate) in the PFS summary.

CBR16 and CBR24

Breast cancer patients will also have CBR16 and CBR24 summarized by dose level and also by cancer subtype (TNBC, HR+/HER2-, HER2+). CBR16 is defined as the proportion of subjects with best overall response of CR or PR or with SD for at least 16 weeks. CBR24 is defined as the proportion of subjects with best overall response of CR or PR or with SD for at least 24 weeks. CBR16 and CBR24 will only be calculated for subjects in the REP.

SD Duration is defined as the time interval from the start of the treatment to the date of subsequent PD or on-treatment death. In the absence of PD or on-treatment death before the analysis cut-off date, it is the time from the start of treatment to the date of the last adequate tumor assessment before the cut-off date.

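### The SAP adds a plain descriptive summary of duration of response beside Kaplan-Meier; its mean is too low whenever a responder is censored, and its median can be (minor)

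*SAP*

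**What the plan says.** SAP 13.1.2 (Secondary Efficacy Endpoints) names Kaplan-Meier as the estimator: "Estimates of time-to-event endpoints (DOR, TTR, PFS, and OS) will be obtained using the Kaplan-Meier method". Medians with 95% confidence intervals, curves and a swim lane plot for DOR are planned. The same section adds a second summary: "DOR and TTR will also be summarized using descriptive statistics for confirmed objective responders". Core 11.3.1 (Efficacy Analysis Methods) contains the same provision.

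Three further statements fix what that second summary would contain.

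- **Who is included** (SAP 13.1.2): "DOR is only calculated for subjects in the REP who have a confirmed objective tumor response". Having an event is not a condition.
- **What value a subject without an event carries** (SAP 13.1.2, with Table 2): "Subjects who neither progress nor die will be censored on the date of their last tumor assessment".
- **What descriptive statistics are** (SAP 10.1): "Continuous data will be summarized using number of non-missing values (n), mean, median, standard deviation, and median and range values".

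The section also promises counts of censoring: "Frequencies and percentages will be summarized for event rates and censored observations of the time-to-event endpoints". It provides a range for time to response (TTR), PFS and OS, but not for DOR.

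**The concern.** TTR and DOR are put together in one sentence although they are different kinds of data. Every confirmed responder has an observed time to response, so a mean and median of TTR are sound. DOR is right-censored: a responder without progression or death has only a lower bound. Averaging that bound with completed durations understates DOR.

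The SAP does not do this for PFS or OS, which are also censored and get no plain descriptive summary. Only DOR is treated this way.

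At stake is a second set of DOR figures beside the Kaplan-Meier results, in tables that SAP section 1 says will support publications and FDA submissions. Small cells are the most exposed. SAP 10.1 splits tables by dose level and cancer type. If the only confirmed responder in a cell is censored, the Kaplan-Meier median cannot be estimated, but the descriptive block would still print that subject's follow-up time as the median DOR.

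**Working it through.** The documents state no DOR figure, so there is nothing to reproduce. The check has two parts.

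**1. What the text produces.** SAP 13.1.2 gives each censored responder a numeric duration, which is therefore a non-missing value under SAP 10.1. Nothing in either document excludes it, flags it or gives a rule for it. On the plain reading it enters n, mean, median, SD and range as if complete. A censored time is never longer than the duration it stands for, so the substitution can only lower the mean.

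**2. How large the error can be.** These assumptions are not from the documents: DOR is exponential with true median 6 months, so the true mean is 6/ln 2 = 8.66 months, and censoring is independent.

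- *Mean.* For a subject with follow-up C, the expected observed time is 8.66 × P(event by C). Averaging over subjects, plain mean = (1 − c) × 8.66, where c is the censored fraction. With c = 0.135 this is 0.865 × 8.66 = 7.49. With c = 0.542 it is 0.458 × 8.66 = 3.97.
- *Median.* The plain median t solves S(t) × G(t) = 0.5, where S is the DOR survival function and G the probability of still being under follow-up. If nobody is censored before 6 months, G(6) = 1 and t = 6, so there is no bias. With follow-up uniform on 0 to 12 months, G(t) = 1 − t/12. At t = 3.26, S = 2^(−3.26/6) = 0.686 and G = 0.728, with product 0.50.

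Simulation (400,000 draws per scenario; Kaplan-Meier median from the first 40,000), in months:

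| Censoring | Censored | KM median | Plain median | Plain mean | Events-only median | Events-only mean |
|---|---|---|---|---|---|---|
| None | 0% | 5.97 | 5.99 | 8.63 | 5.99 | 8.63 |
| Exponential | 10.1% | 6.02 | 5.39 | 7.77 | 5.40 | 7.77 |
| Exponential | 19.9% | 6.02 | 4.78 | 6.92 | 4.79 | 6.93 |
| Exponential | 29.9% | 6.00 | 4.20 | 6.06 | 4.20 | 6.06 |
| Exponential | 50.0% | 5.99 | 3.01 | 4.34 | 3.00 | 4.33 |
| Uniform 12–24 months | 13.5% | 6.02 | 6.00 | 7.49 | 4.90 | 6.05 |
| Uniform 6–24 months | 21.1% | 6.02 | 6.01 | 6.84 | 4.36 | 5.44 |
| Uniform 3–12 months | 44.0% | 6.00 | 4.47 | 4.85 | 2.84 | 3.37 |
| Uniform 0–12 months | 54.2% | 6.07 | 3.26 | 3.97 | 2.54 | 3.17 |

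The Kaplan-Meier median stays between 5.97 and 6.07 throughout. The plain mean is low in every row with censoring. The plain median is low only where some censoring falls before 6 months. The events-only columns cover the other possible reading, in which only responders with an event are summarised. That reading is also biased low: about equally under exponential censoring, and more so under all four uniform patterns.

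**The case against.** The SAP never says in words that censored durations count as complete. That is an inference from 10.1 and 13.1.2 read together. This is fair, but the conclusion does not depend on it, because an events-only summary is also biased low.

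A reader might infer more: that the descriptive median is always wrong, or that most responders will still be in response at the data cut. The documents support neither. The median is unbiased when all censoring comes after the true median, as in the 12–24 and 6–24 month rows. No section gives a censored fraction, and several features point towards less censoring at the final analysis. SAP 4.3 continues imaging until progression after treatment stops and places study completion about 2 years after the last enrolment. Table 2 has a single censoring rule for DOR, with none for new anticancer therapy or for events in follow-up. Early withdrawal, or an administrative data cut of the kind SAP 7.1 allows, could still leave responders censored.

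The safeguards also count. A reader will see the Kaplan-Meier median with its confidence interval, the number censored and a swim lane plot beside the descriptive figures. Confirmed responders are few: Protocol 1.3.4.2 reports 2 of 92 at 30 November 2019, and SAP 4.2 gives a final total of 99 treated, 3 of them in Part B. SAP section 1 allows analyses to be dropped if numbers are inadequate. No test or decision rule uses this summary.

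Finally, simply deleting DOR from the sentence would remove the only DOR range the SAP provides. That stands, and the fix must allow for it.

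**Conclusion.** The point holds, as a minor one. Followed as written, the plan gives a descriptive mean DOR that is too low if any confirmed responder is censored, and a descriptive median that is too low when censoring falls before the true median. Across the uniform follow-up patterns tried, the plain median ran from no bias (6.0) to about 3.3 against a true 6 months, and the plain mean from about 7.5 to 4.0 against 8.66. Exponential censoring at 50% halves both. These sizes rest on assumed exponential durations, independent censoring and a true median of 6 months. The direction for the mean does not. With no censored responder there is no error.

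The Kaplan-Meier DOR results are unaffected, and nothing here touches the primary endpoint. The realistic harm is a misleading figure in a small dose or tumour cell where the Kaplan-Meier median is not estimable.

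**What to change.** In SAP 13.1.2:

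1. Limit the descriptive-statistics sentence to TTR.
2. Report DOR by Kaplan-Meier only.
3. Add DOR to the sentence that provides ranges for TTR, PFS and OS, with censored values marked by a plus sign.
4. List individual durations with censoring status.

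The change departs from Core 11.3.1. Section 9.2 of the protocol Module lets the SAP supersede the Core where they conflict, so no Core amendment is needed, but the departure should be noted. The cost is two edited SAP sentences, one listing and one fewer table block. No new data are required.

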13.1.3 Efficacy Measures during Follow-up

Following the completion of study treatment, subjects with progressive disease will enter the follow-up period for monitoring of survival; subjects with SD, PR, or CR will enter the follow-up period for monitoring of DOR and PFS. Once a subject experiences progressive disease, they will continue to be monitored for survival.

13.1.4 Eastern Cooperative Oncology Group (ECOG) Performance Status

Eastern Cooperative Oncology Group (ECOG) performance status (0, 1, 2, 3, 4, and 5) will be presented in a listing.

14. Pharmacokinetic, Immunogenicity, and Pharmacodynamic Assessments

14.1 PK Assessments

A third-party PK vendor will conduct all analyses related to PK data. Details of the PK analyses will be provided in a separate PK analysis plan.

14.2 Immunogenicity Assessments

Serum samples will be collected from study participants, as described in the protocol to assess the immunogenicity of CX-2009. Samples will be initially screened for anti-drug antibodies (ADA). If the sample is found to be ADA positive in the screening assay, a confirmatory assay and a titer assay will be performed to further characterize antidrug antibodies.

Samples will be drawn at times indicated in the CTMX-M-2009-001 Protocol Module.

Immunogenicity results will be listed by part and dose cohort. ADA statistical analyses will be detailed and summarized in a separate report.

15. Exploratory Analyses

15.1 Pharmacodynamics and Exploratory Biomarkers

The overall goal of the biomarker portion of CTMX-M-2009-001 is to explore

- A) Probable mechanistic proof of concept, and
- B) Potential predictive markers associated with CX-2009 clinical activity.

This information will help to further build the translational program for the development of Exploratory studies will evaluate:

- Probable activation in tumors compared to a peripheral normal tissue compartment (blood);
- The potential link between markers, such as the target of CX-2009 (i.e., CD166), and mitotic markers (e.g., Ki-67), and the biological activity of CX-2009; and
- The presence of activated proteases in the human TME capable of removing the peptide mask and thereby activating the Probable-Tx.

If the exploratory study results are presented in the CSR, a description of the methodology will be included there.

15.2 Additional Exploratory Analyses

Upon review of the data, additional exploratory analyses may be conducted. If these are presented in the CSR, a description of the methodology will be included there.

16. References

International Conference on Harmonization (ICH) guideline "Statistical principles for Clinical trials": E9, 1998.
